#### Primary endpoint

The primary endpoint is time to the first occurrence of any of the following adjudicated components of the composite endpoint (**43**-point MACE): CV death (~~including fatal stroke, fatal MI, and sudden death~~), non-fatal MI (~~excluding silent MI~~), **or** non-fatal stroke, ~~hospitalisation for unstable angina pectoris~~.

Patients without occurrence of a specific endpoint (composite endpoint or individual components) will be considered censored at their last documented study visit. If any measurement of laboratory data or ECG is available after the last visit of a patient, the date of the respective measurement will be used for censoring of the CV endpoint. If any measurement of eGFR is available after the last visit of a patient, the date of the respective measurement will be used for censoring of the renal endpoint. For all endpoints including the component CV (renal) death, adjudicated CV (renal) death will be counted even if occurred thereafter.

### 7.2 NULL AND ALTERNATIVE HYPOTHESES

~~An interim analysis will be performed at the one-sided alpha level of 1.0%, the final analysis at the one-sided alpha level of 2.12%. At the interim analysis MACE endpoints will be tested~~

Proprietary confidential information.

© 2016 Boehringer Ingelheim International GmbH or one or more of its affiliated companies. All rights reserved.

This document may not - in full or in part - be passed on, reproduced, published or otherwise used without prior written permission.

in a pre-specified order, at the final analysis also the composite renal endpoint will be tested for superiority. The experimentwise (multiple) level alpha is controlled with the following three step gatekeeping hierarchy within the interim and final analysis, respectively.

**No confirmatory interim analysis for efficacy endpoints will be performed.** For the final analysis, the first hypothesis (non-inferiority of the primary endpoint) will be tested at the one-sided alpha-level of 2.12% **2.5%**. In case of significance, the null hypothesis is rejected in a confirmatory sense and the next set of hypotheses (two separate hypothesis tests) will be tested: a) test of the primary endpoint for superiority and b) test of the composite renal endpoint for superiority. To adjust for multiplicity the truncated Hochberg **a sequentially rejective** multiple test procedure will be applied ([R16-4473](#)) with a selected gamma of 0.5 ([R12-4087](#)). Both one-sided hypotheses  $H_{0(\text{Sup1})}$  and  $H_{0(\text{Sup2})}$  will be tested separately, **at the initial alpha-levels of 0.2\*alpha for 3-point MACE and 0.8\*alpha for the composite renal endpoint, respectively.** If both null hypotheses cannot be rejected at these initial alpha-levels, the procedure stops and for none of these endpoints superiority can be declared. After having shown superiority for one of these endpoints, the used alpha can be shuffled to the other test: If  $H_{0(\text{Sup2})}$  is rejected at the alpha-level of 0.8\*alpha, then  $H_{0(\text{Sup1})}$  can be tested at the full alpha-level of 2.5% (one-sided). If  $H_{0(\text{Sup1})}$  is rejected at the alpha-level of 0.2\*alpha, then  $H_{0(\text{Sup2})}$  can be tested at the full alpha-level of 2.5% (one-sided). If both tests are significant at the one-sided alpha level of 1.59% each, superiority of both endpoints (4-point MACE and composite renal endpoint) has been demonstrated. If not, superiority can only be claimed for the endpoint significant at the alpha-level of 1.06%. If superiority of both, the 4-point MACE and the composite renal endpoint has been demonstrated at the one-sided alpha-level of 1.59% each, then superiority of the 3-point MACE can be tested at the alpha-level of 2.12%. If superiority of only one of these endpoints (4-point MACE or composite renal endpoint) has been demonstrated at the one-sided alpha level of 1.06%, then superiority of the 3-point MACE can be tested at the alpha-level of 0.53%.

~~At the interim analysis superiority of the composite renal endpoint will not be tested and therefore all tests on MACE can be performed in the pre-specified order at the alpha-level of 1.0%.~~

If a step is not significant, all subsequent steps may not be interpreted in a confirmatory sense. The sequence of tests is as follows:

1st step:

The primary endpoint (**4** **3**-point MACE) is time to the first occurrence of any of the following adjudicated components of the composite endpoint: CV death (~~including fatal stroke, fatal MI, and sudden death~~), non-fatal MI, **or** non-fatal stroke, ~~hospitalisation for unstable angina pectoris~~.

$H_{0(\text{NI})}$ :  $\text{HR}_{\text{linagliptin vs. placebo}} \geq 1.3$

(Interpretation of  $H_{0(\text{NI})}$ : Regarding the time to first occurrence of the primary endpoint, the risk (expressed as hazard ratio (HR)) for linagliptin relative to placebo is at least 30% higher.)

Proprietary confidential information.

© 2016 Boehringer Ingelheim International GmbH or one or more of its affiliated companies. All rights reserved.

This document may not - in full or in part - be passed on, reproduced, published or otherwise used without prior written permission.

vs.

$H_{1(NI)}$ :  $HR_{linagliptin \text{ vs. placebo}} < 1.3$

( $H_{1(NI)}$ : Regarding the time to first occurrence of the primary endpoint, the risk for linagliptin relative to placebo is less than 30% higher, i.e. linagliptin can be regarded as non-inferior.)

2nd step:

If the null hypothesis of non-inferiority (1st step) can be rejected, then in a second step two confirmatory tests on superiority will be performed ~~at the final analysis~~:

- time to first occurrence of the primary endpoint (4 ~~3~~-point MACE)
- time to first occurrence of the composite renal endpoint

~~At the interim analysis superiority of the composite renal endpoint (i.e.  $H_{0(Sup2)}$ ) will not be tested.~~

$H_{0(Sup1)}$ :  $HR_{linagliptin \text{ vs. placebo}} \geq 1$

( $H_{0(Sup1)}$ : Regarding the time to first occurrence of the primary endpoint, the risk for linagliptin relative to placebo is higher.)

vs.

$H_{1(Sup1)}$ :  $HR_{linagliptin \text{ vs. placebo}} < 1$

( $H_{1(Sup1)}$ : Regarding the time to first occurrence of the primary endpoint, the risk for linagliptin relative to placebo is lower.)

$H_{0(Sup2)}$ :  $HR_{linagliptin \text{ vs. placebo}} \geq 1$

( $H_{0(Sup2)}$ : Regarding the time to first occurrence of the composite renal endpoint, the risk for linagliptin relative to placebo is higher.)

vs.

$H_{1(Sup2)}$ :  $HR_{linagliptin \text{ vs. placebo}} < 1$

( $H_{1(Sup2)}$ : Regarding the time to first occurrence of the composite renal endpoint, the risk for linagliptin relative to placebo is lower.)

To adjust for multiplicity ~~at the final analysis the truncated Höchberg~~ **a sequentially  
rejective** multiple test procedure will be applied.

3rd step:

~~If superiority of the primary endpoint (4 point MACE) and/or the composite renal endpoint has been demonstrated, then as a further confirmatory test superiority is tested with respect to time to first occurrence of the 3-point MACE.~~

Proprietary confidential information.

© 2016 Boehringer Ingelheim International GmbH or one or more of its affiliated companies. All rights reserved.

This document may not - in full or in part - be passed on, reproduced, published or otherwise used without prior written permission.

$H_0(Sup3): HR_{linagliptin \ vs. \ placebo} \geq 1$

( $H_0(Sup3):$  Regarding the time to first occurrence of the 3-point MACE, the risk for linagliptin relative to placebo is higher.)

vs.

$H_1(Sup3): HR_{linagliptin \ vs. \ placebo} < 1$

( $H_1(Sup3):$  Regarding the time to first occurrence of the 3-point MACE, the risk for linagliptin relative to placebo is lower.)

### 7.3 PLANNED ANALYSES

The primary analyses (including all confirmatory tests described in [Section 7.2](#)) will be performed on the ~~full analysis set (FAS)~~ **Treated Set (TS)**. The ~~FAS~~ **TS** will consist of all ~~randomized~~ patients who were treated with at least one dose of study drug.

For the primary and key secondary endpoints a ‘classical intention to treat (ITT) analysis on the ~~FAS~~ **TS**’ will be done. That means that:

- the analysis set consists of the ~~FAS~~ **TS**,
- the allocated study treatment at randomization will be used for the analysis (‘as randomized’),
- all events which occur until study end will be taken into account.

A per protocol set (PPS) of patients following the trial protocol in essential criteria will be created for sensitivity analyses. Patients included in the ~~FAS~~ **TS** who have important protocol violations will be excluded from the PPS. A protocol violation (PV) will be considered important if it can be expected to have a distorting influence on the assessment of the primary endpoint.

Important protocol violations include:

- Randomized study drug: incorrect study drug taken.
- Severe violation of treatment compliance (defined as compliance with study treatment < 80% for more than 50% of the time between randomization and first endpoint (CV death, non-fatal MI, non-fatal stroke, ~~hospitalisation for unstable angina pectoris~~).
- Non-adherence to other specifications of the protocol that could bias the primary composite endpoint (e.g. limited life expectancy (< 5 years) at randomization due to various medical conditions)

Additionally a ‘30-day treatment’ **on-treatment** set (**OS**) of patients will be created for sensitivity analysis. The ‘30-day treatment’ **OS** set will include all patients with minimum treatment duration of 30-days.

All patients treated with at least one dose of study drug (the Treated Set) will be included in the safety evaluation. ~~In case only randomized patients take study drug, this set is identical to the FAS;~~ the safety analyses will be displayed ‘as randomized’.

Proprietary confidential information.

© 2016 Boehringer Ingelheim International GmbH or one or more of its affiliated companies. All rights reserved.

This document may not - in full or in part - be passed on, reproduced, published or otherwise used without prior written permission.

Data recorded on entry into the study and at randomization will be summarized and compared using univariate descriptive statistics.

Additional analyses will be explored in ~~specific~~ subgroups, e.g. depending on characteristics at baseline with respect to the primary and key secondary endpoints. **Examples of Covariates that will be explored include:**

- Region (North America, Europe, Asia etc.)
- Age (<65,  $\geq$  65 years)
- Systolic and diastolic blood pressure ( $<140$  and  $<90$  mmHg,  $\geq 140$  or  $\geq 90$  mmHg)
- Gender (male, female)
- Prior anti-diabetic treatment (~~none, monotherapy, combination therapy~~ **insulin, no insulin**)
- eGFR  $< 60$  mL/min/1.73 m^2 at baseline
- **Prevalent kidney disease defined as eGFR  $< 60$  mL/min/1.73 m^2 at baseline and/or UACR  $> 300$  mg/g creatinine at baseline**

Further details will be given in the trial statistical analysis plan (TSAP).

### 7.3.1 Primary analyses

A classical ITT-approach on the FAS **TS** will be performed as described above. For the primary analysis a Cox proportional hazards regression model of time to the first event with randomized treatment and geographical region as factors will be applied. Kaplan-Meier estimates by treatment group will be displayed. The confirmatory test approach is outlined in [Section 7.2](#).

No centre effect will be included into the Cox models, as the centre size is expected to be small. Furthermore, due to the low event rate there would not be a sufficient number of events per centre for the analysis of a centre effect and a centre by treatment interaction.

For the primary and key secondary endpoints, sensitivity analyses will be done on the PPS, for the '~~30 days treatment~~' set **OS** and as ~~an 'on treatment'~~ a '**TS+30**' analysis as described below. These sensitivity analyses will be performed based on the corresponding patient sets for the time patients are on-treatment + 30 days after permanent treatment discontinuation or end of observation, whichever comes first. The '~~on treatment analysis~~' '**TS+30**' analysis will be performed on the FAS **TS** (consisting of all ~~randomized~~ patients who were treated with at least one dose of study drug) with censoring at the time patients are on treatment + 30 days after permanent treatment discontinuation or end of observation, whichever comes first.

For these sensitivity analyses, the randomized study treatment ('as randomized') will be used for treatment assignment.

To check the proportional hazards assumption, Schoenfeld residuals will be plotted for each covariate versus time; in addition,  $\ln(-\ln(S(t)))$  will be plotted vs. time and checked for

Proprietary confidential information.

© 2016 Boehringer Ingelheim International GmbH or one or more of its affiliated companies. All rights reserved.

This document may not - in full or in part - be passed on, reproduced, published or otherwise used without prior written permission.

parallelism. As a further assessment the interaction of covariates with time will be investigated. In case the proportionality assumption does not hold, a stratified log-rank test will be performed.

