As the study population of this trial are patients with high CV risk, all with various degrees of end-organ damage (i.e., renal impairment) it is conceivable that the study will include patients at all stages of T2DM duration since in fact many patients are being diagnosed with T2DM for the first time at the occasion of a CV event [[R12-1135](#)]. Therefore, antidiabetic treatment naïve, as well as patients with all kind of approved background antidiabetic treatment (including insulins) are eligible. The only exceptions are patients on DPP-4 inhibitors and/or GLP-1 receptor agonists and/or sodium glucose linked transporter (SGLT-2) inhibitors. Taking into consideration linagliptins mode of action, there is not an option in this trial to combine study drug (i.e., placebo or linagliptin) with a GLP-1 receptor analogue as the DPP4 inhibitor and GLP1 receptor analogue combination is not approved or indicated (per label of all GLP-1 products and DPP4 inhibitors). Also concomitant use of an SGLT-2 inhibitor is not allowed since this is a new class of drug that is and hitherto undescribed in terms of CV benefit-risk ratio in order to reduce complexity of interpretation of study outcome. Further, as this trial would like to address the impact on CV outcomes of linagliptin compared to placebo in a high CV risk population, some with high degree of renal impairment, where most likely the use of SGLT-2 inhibitors will be restricted, SGLT-2 inhibitors would only be an applicable therapy for a subset of the study cohort.

The study has two arms: linagliptin or placebo as add-on to antidiabetic treatment naive patients or other allowed antidiabetic treatments. The study design is described in more detail in [Section 3.1](#).

Proprietary confidential information.

© 2016 Boehringer Ingelheim International GmbH or one or more of its affiliated companies. All rights reserved.

This document may not - in full or in part - be passed on, reproduced, published or otherwise used without prior written permission.

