#### 4.2.2 Restrictions

##### 4.2.2.1 Restrictions regarding concomitant treatment

The use of other ~~DPP4~~ **DPP4** inhibitors and/or injectable GLP-1 receptor agonists and/or SGLT-2 inhibitors (next to background therapy and any additional anti-diabetic therapy) will be prohibited during the course of the study.

If any restricted treatments or any other concomitant drugs interfering with the study medication are given during the conduct of the trial, the study medication can be discontinued temporarily, or if needed permanently.

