#### **6.2** IMPORTANT PROTOCOL VIOLATIONS

Data discrepancies and deviations from the CTP will be identified for all patients randomized and/or treated.

A protocol violation (PV) is defined as important, if it affects the rights or safety of the trial patients or if it can potentially influence the primary endpoint for the respective patients in a way that is neither negligible nor in accordance with the trial objectives.

The category of important PVs, which can potentially influence the primary or key secondary outcome measures, forms the basis for the decision of whether a patient belongs to a patient analysis set.

The following table displays the categories considered to be important protocol violations. If the data indicate further important PVs, this table will be supplemented accordingly, with the latest modification made prior to database lock.

The important PVs will be described in the Clinical Trial Report (CTR). A listing of patients who had the medication code broken will be provided.

A table showing the number of patients and frequency with violation of in- or exclusion criteria will be provided.

Table 6.2: 1 Important Protocol Violations

Category / Code		Description	Comment/Example	Affects rights (R)/ safety (S) or primary/ key secondary outcome (E)	Excluded from
A		Entrance Criteria Not N			
	A.1	Inclusion criteria violate			
	A1.1	No type 2 diabetes	Inclusion criterion IN1 ticked "No"	Е	PPS
	A.2	Exclusion criteria violat	ted		
	A.2.1	Type I diabetes	Exclusion criterion EX1 ticked "Yes"	Е	PPS
	A.2.2	Severe renal impairment (eGFR < 15 ml/min/1.73 m²) or ESRD at Visit 1 and/or the need for maintenance dialysis	Exclusion criterion EX4 ticked "Yes" Or eGFR < 15 ml/min/1.73 m² at visit 1	Е	PPS
	A.2.3	Pre-planned coronary artery re-vascularisation (PCI, CABG)	Exclusion criterion EX6 ticked "Yes"	Е	PPS
	A.2.4	Specific exclusion criterion for premenopausal women violated	Exclusion criterion EX10 ticked "Yes"	R/S	None

Table 6.2: 1 Important Protocol Violations (cont.)

Cate Cod	egory / e	Description	Comment/Example	Affects rights (R)/ safety (S) or primary/ key secondary outcome (E)	Excluded from
	A.2.5	Patients considered unreliable by the investigator for safe participation in the study	Exclusion criterion EX11 ticked "Yes"	Е	PPS
	A.2.6	Acute coronary syndrome (ACS), diagnosed ≤ 2 months prior to Visit 1	Exclusion criterion EX12 ticked "Yes"	Е	PPS

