	A.2.7	Stroke or transient ischemic attack (TIA) ≤ 3 months prior to Visit 1	Exclusion criterion EX13 ticked "Yes"	Е	PPS
В	Γ	Informed Consent			
	B1	Informed consent not available	Inclusion criterion IN7 ticked "No" Or Date of informed consent missing Or No signature on patient's "Declaration of Informed Consent" (to be identified by CRA)	R/S	All

Table 6.2: 1 Important Protocol Violations (cont.)

Cate	egory / le	Description	Comment/Example	Affects rights (R)/ safety (S) or primary/ key secondary outcome (E)	Excluded from
	B2	Informed consent given too late	Date of informed consent for the study not obtained prior to any study related procedure  Minimum requirement for initial informed consent ≤ date of visit 1/date of any study procedure	R/S	None
C		Trial medication and	randomisation		
	C1	Incorrect Trial Medication Taken			
	C1.1	No study medication taken	Patient randomised, but no study medication taken	Е	PPS, TS

Table 6.2: 1 Important Protocol Violations (cont.)

Category / Code	Description	Comment/Example	Affects rights (R)/ safety (S) or primary/ key secondary outcome (E)	Excluded from
C1.2	Randomisation not for	Wrong medication (different medication than the patient was randomised to) taken for more than 20% of the overall treatment duration (between randomisation and first outcome event) of a patient.  This is identified by the medication kit number recorded in eCRF as well as the medication kit number as assigned by IRT.  Can also be manually identified by investigator or CRA.  Can only be finally judged after DBL since unblinding information is required.	E	PPS
C2.1	Treated before randomisation	Date of randomisation after date of study medication intake at visit 2; Or Patient treated according to eCRF, but not randomised according to IRT.	Е	PPS
C3	Non-compliance	-		

Table 6.2: 1 Important Protocol Violations (cont.)

Cat		Description	Comment/Example	Affects rights (R)/ safety (S) or primary/ key secondary outcome (E)	Excluded from
	C3.1	Non-compliance with criteria for removal from the trial	A missing pregnancy test does not qualify as IPV.	R/S	None
D		Concomitant Medication	Not Applicable		
E		Missing data	Not Applicable		
F		Incorrect timing	Not Applicable		
G		Trial specific protocol violations			
	G1.1	Previous participation (randomisation) within this study		E/S/R	PPS
	G1.2	Serious non- compliance potentially affecting primary endpoint		E/S/R	PPS*

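### Do the supportive analyses of 3-point MACE need a restricted-drug exclusion and a version of TS+30 that censors at treatment interruptions?

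*Protocol*

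**What the plan says.** Protocol 7.3.1 plans three sensitivity analyses of the primary and key secondary endpoints: on the PPS, on the on-treatment set (OS, at least 30 days of treatment) and as TS+30. All three are limited to time on treatment plus 30 days. TS+30 applies "censoring at the time patients are on treatment + 30 days after permanent treatment discontinuation or end of observation, whichever comes first". The x-day censoring rules in SAP 6.8.3 count from last intake of study drug. Protocol 3.3.4.1 allows restarts at any time and limits neither the number nor the length of interruptions.

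Protocol 4.2.2.1 names other DPP-4 inhibitors, injectable GLP-1 receptor agonists and SGLT-2 inhibitors, whose use "next to background therapy and any additional anti-diabetic therapy) will be prohibited during the course of the study". Protocol 2.1 bars SGLT-2 inhibitors partly "in order to reduce complexity of interpretation of study outcome". Category D of SAP Table 6.2:1 nevertheless reads "Concomitant Medication Not Applicable".

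Under Protocol 7.3 a violation "will be considered important if it can be expected to have a distorting influence on the assessment of the primary endpoint". The examples there include "Severe violation of treatment compliance (defined as compliance with study treatment < 80% for more than 50% of the time between randomization and first endpoint" and, as a catch-all, "Non-adherence to other specifications of the protocol that could bias the primary composite endpoint". The SAP table excludes serious non-compliance from the PPS under code G1.2, and its footnote points to a separate document for details. On additions, SAP 6.2 says: "If the data indicate further important PVs, this table will be supplemented accordingly, with the latest modification made prior to database lock".

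**The concern.** The primary claim is non-inferiority, and the primary analysis counts every event to trial end whether or not the patient is on drug. If linagliptin raised risk, off-drug time in that arm, or open-label DPP-4 inhibitor use on placebo, would pull the hazard ratio towards 1 and make the claim easier. The PPS and TS+30 are where a reader would look to judge this, and as visible they look incomplete in three ways:

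- Prohibited drugs have no PPS code.
- The protocol's 80%/50% compliance rule does not appear in the SAP table.
- TS+30 keeps interruptions of any length if the patient restarts. No sentence says so for TS+30, but it follows from the rules on permanent discontinuation, last intake and unlimited interruptions.

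The suggested remedies would be a restricted-drug code, the compliance rule written into the table, and a TS+30 variant censored 30 days after the start of the first gap longer than 30 days.

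**Working it through.** **The plan's own figure.** Events for 90% power with margin 1.3, true HR 1, one-sided 2.5% and 1:1 allocation (Protocol 7.1 and 7.6): 4 × (1.960 + 1.282)² / (ln 1.3)² = 611, as stated.

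**What the existing rules already catch.** Protocol 4.2.1 leaves the three drug classes out of permitted glycaemic medication. It adds that patients who need medication beyond what the protocol specifies should stop study treatment and stay in the trial. If that stop is permanent, Protocol 7.3.1 censors the patient 30 days later in the PPS, OS and TS+30 alike. What is left is drop-in with study drug continued or only paused. Protocol 4.2.2.1 is more permissive, allowing temporary or permanent discontinuation. The two sections should be reconciled, but they are clinical-management text and no view is taken here on which should govern.

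**Size of the dilution.** The documents give no share of time without treatment contrast, so q = 5%, 10% and 20% of retained follow-up are assumptions, as is an on-drug HR of 1.30. With D events,

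P(upper 95% limit < 1.3) = Φ[(ln 1.3 − ln HR) × √D / 2 − 1.96].

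- Linagliptin off drug, HR = 1.3 − 0.3q = 1.285, 1.270, 1.240. With D = 611, P = 3.5%, 4.7%, 8.4%, against 2.5% undiluted.
- DPP-4 inhibitor on placebo with the same effect as linagliptin, HR = 1.3/(1 + 0.3q) = 1.281, 1.262, 1.226. P = 3.8%, 5.5%, 10.8%. Here q counts only drop-in not already censored.
- On-drug HR 1.0, the planning assumption: HR stays 1.0 for every q, and P stays 90%.

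**What the PPS and the variant would each do.** Assume a proportion g of patients in each arm (15%, 30%, 60%) has one gap, with start and end at two random times in follow-up. The mean gap is then one third of follow-up, so q = g/3. Gap timing is taken as unrelated to risk, and TS+30 has 611 events.

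For the PPS, treat gap time as non-compliant and apply the 80%/50% rule to total follow-up, as an approximation. A quarter of gaps exceed half of follow-up, and these hold half of all gap time. The remaining share is (g/6)/(1 − g/4), with 611 × (1 − g/4) events.

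For the variant, follow-up is simulated as uniform over 18 to 54 months (54-month trial, 36-month recruitment). Events are 611 × share of follow-up kept × (1 + new HR)/(1 + TS+30 HR). For g = 30%: 611 × 0.816 × 2.297/2.270 = 504.

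| | g = 15% | g = 30% | g = 60% |
|---|---|---|---|
| TS+30: q | 5% | 10% | 20% |
| TS+30: HR | 1.285 | 1.270 | 1.240 |
| TS+30: P | 3.5% | 4.7% | 8.4% |
| PPS: q | 2.6% | 5.4% | 11.8% |
| PPS: HR | 1.292 | 1.284 | 1.265 |
| PPS: events | 588 | 565 | 519 |
| PPS: P | 3.0% | 3.5% | 5.0% |
| Variant: follow-up kept | 0.908 | 0.816 | 0.632 |
| Variant: HR | 1.299 | 1.297 | 1.292 |
| Variant: events | 558 | 504 | 395 |
| Variant: P | 2.6% | 2.7% | 2.9% |

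The ratio of upper limit to estimate, exp(1.96 × 2/√D), is 1.172 at 611 events. In the variant it widens to 1.181, 1.191 and 1.218.

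**The case for a change.** The strongest case for a change is that it is cheap and fits principles the SAP already accepts. Code C1.2 excludes from the PPS a patient on the wrong trial medication for more than 20% of treatment duration. Open-label DPP-4 inhibitor use on placebo erodes the contrast in a similar way and has no code. Concomitant drugs and tablet counts are collected, and SAP 7.8.1.1 already derives exposure without treatment gaps for cancer events. The PPS, OS and TS+30 share the same permanent-discontinuation window, so none of them censors at an interruption, and the compliance rule that would help the PPS cannot be traced in the visible table. The catch-all and the option to extend the table state no rule for these drugs.

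The description stands; the case for changing the plan does not.

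- **Restricted-drug code.** It would exclude patients on drug use after randomisation and before the first event. Longer event-free time gives more opportunity for such use, and use triggered by poor glycaemic control may differ by arm. Statisticians would reasonably disagree on whether that PPS is better.
- **Compliance rule.** It stands in Protocol 7.3, on which the SAP says it is based. Code G1.2 covers serious non-compliance and cites a further document. Nothing shows the rule was dropped; at most a cross-reference is missing.
- **TS+30 variant.** The simulated gain is its best case, because gap timing was unrelated to risk. Patients who interrupt when they become ill would be censored informatively.

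Nor can it be said that nothing similar is planned. The public copy does not show SAP 7.4.3 and 7.4.4, the overview table of primary-endpoint analyses, the PPS and OS definitions or the G1.2 document. SAP Section 4 records that study populations and censoring methods were separated and clarified after regulatory advice.

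**Conclusion.** No change is called for. Leaving category D without a code is a gap that the open violation definition and the pre-lock update of the table allow the trial team to fill. The missing compliance threshold is at most a missing cross-reference. TS+30 follows its own definition; keeping interruptions in, rather than censoring at them, is a fair trade-off between dilution on one side and lost events and informative censoring on the other.

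At 10% off-drug time and an on-drug HR of 1.30, the variant would lower the chance of an upper limit below 1.3 from 4.7% to 2.7%, at a cost of 611 − 504 = 107 events. A PPS applying the protocol's compliance rule already brings it to about 3.5%. At 20% off-drug time the figures are 8.4%, 2.9% and 5.0%, and the variant loses 216 events, about a third. These figures rest on assumed off-drug shares, a constant hazard, no carry-over effect and gaps unrelated to risk. The visible text sets no success criterion for the sensitivity analyses, so the percentages describe how sensitive a check is and are not decision errors. The non-inferiority test, its one-sided 2.5% level and the event target are unaffected.
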